4.1.1 SABR Dose

The SABR dose and fractionation scheme is generated to deliver a potent dose to ablate the targeted lesions and at the same time maximize an immune response. Since multiple studies have shown an influx of lymphocytes and monocytes after tumor irradiation [12, 17, 18, 90] and since these cells play a critical role in antigen presentation and initiation of an adaptive immune response, multiple fraction irradiation which would kill these infiltrating immunocytes, is discouraged. Therefore a single fraction or a three fraction treatment regimen is allowed, and a single fraction treatment is preferred over three fractions. Due to normal organ toxicity and limits of dose constraints, sometimes a three fraction treatment must be undertaken and in those cases it is recommended that the treatment course is completed within 7-10 days (preferably 5 business days). Radiation dose-(immune) response studies have shown a linear increase in immune response with increased dose per fraction of radiation without demonstration of a plateau [17, 19, 90, 91]. Two studies comparing 15Gy x 1 vs 5Gy x3, and 20Gy x1 vs 5Gy x4 have shown a superior immune response generated by the single fraction radiation [17, 90]. Clinical experience with oligometastatic patients treated at 1-5 sites of disease has also showed an increase in progression free survival with the increasing radiation dose per fraction [92]. A dose of less than 7.5 Gy per fraction has demonstrated lower induction of systemic IFN- γ producing cells [91], and a previous phase II study of mRCC patients treated with HD IL-2 and single fraction of 8Gy irradiation to a single lesion did not show an overall improvement in response rate [93]. Therefore 8Gy per fraction is the lowest permitted dose for this study and can be used only when administering the three fraction regimen as described in the prescription dose table below.

The SABR prescription dose will be delivered to the periphery of the planning target volume (PTV, see below for definitions). Investigators will have discretion in choosing from either of the biologically equivalent dose levels using one or three fractions, although a single fraction is preferred over three fraction treatments. Treating physician will have further discretion in selecting the number and location of sites to treat if multiple sites of disease are present. Maximum number of lesions treated is deemed as feasible per the treating radiation oncologist. Physicians will be **REQUIRED** to leave at least one site of disease for the purpose of measuring a radiographic response (see section 6) at a non-treated site, as this is part of the primary endpoint. If left untreated, this site can be treated once patient meets the definition of progressive disease (PD) (see section 6). To clarify the definition of “site”, each site is an area or organ with active extracranial disease (≤ 3 in the liver = one site and ≤ 3 in the lung = one site) identified by CT scan, or PET/CT, within 4 weeks prior to initiation of SABR (up to 2 contiguous vertebral metastasis will be considered a single site of disease). For example: a patient with 4 right axillary lymph nodes, L1-L2 bone metastasis, 3 right lung lesions, 1 left lung lesion, 2 liver lesions, and

T2-T3 bone metastasis would be defined as having 6 sites of disease. Preference should be given to the largest feasible disease site, symptomatic sites and sites where palliative and preventative (i.e. to prevent a pathologic fracture in weight bearing bone, impending cord compression, impending SVC compression etc.) indications are applicable. The gross target/tumor volume (GTV) should be at least 2 cm³ in size, corresponding to roughly a 1.5 cm diameter tumor. This is to ensure that adequate tumor volume and therefore adequate tumor cells (roughly 10⁸ -10⁹ cells/cm³ [94]) are killed for antigen presentation. Treating physicians should choose their dose based on established planning guidelines at their center including their ability to respect normal tissue tolerance listed below. It is not required that all targets be treated with the same dose fractionation. A dose from the following table should be used:

Table 4.1.1 Prescription Dose

Number of Fractions	Total Cumulative Dose Encompassing 95% of Planning Target Volume (Gy)		
	Protocol Compliant	Minor Deviation *	Major Deviation
1	24-27 Gy	≥16 Gy, <24 Gy	<16 Gy
3	33-48 Gy	≥24.5 Gy, <33 Gy	<24 Gy

*This column is protocol compliant for tumors abutting the spinal cord (major deviation remain as listed)

Dose tolerance limits should be adhered to for all treatments. Protocol compliant dose should be used in all cases, if possible. When treating tumors abutting the spinal cord, tolerance limits should not be exceeded. To facilitate this requirement, minor deviation dose ranges listed above in the table will be considered fully compliant for tumors abutting the spinal cord.

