2.0 STUDY OBJECTIVES

This study is a safety lead-in phase II single institution clinical trial using Nivolumab and concurrent SABR to 1-6 metastatic sites in patients with metastatic clear cell renal cell cancer (mccRCC) who have received at least one prior anti-angiogenic therapy. Nivolumab will be dosed intravenously as per the institution guidelines, until disease progression, unacceptable toxicity or other reasons specified in the protocol. No dose modifications for Nivolumab will be allowed. SABR will be administered to 1-6 sites of metastatic disease one week after the first dose of

Nivolumab with a single (24-27 Gy) or three (11-16 Gy/fraction) fractions. The sites of larger (bulky) disease and the sites of symptomatic disease will be prioritized for treatment at the discretion of the treating radiation oncologist.

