4.0 TREATMENT PLAN

4.1 SABR Dose and Techniques

Patients should have at least 1 measurable non-CNS lesions. Lesions receiving SABR will be called “radiated” lesions. “Target” lesions will be selected from non-treated lesions. In any case, there should be at least one (non-CNS) measurable lesion for effect measurement. Prior irradiated lesions (outside of the trial) will be excluded from target lesions. SABR will be administered to 1-6 sites of metastatic disease on the 2 weeks after the second dose of Nivolumab with a single (24-27 Gy) or three (11-16 Gy/fraction) fractions. The sites of larger (bulky) disease and the sites of symptomatic disease will be prioritized for treatment.

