5.2 Procedures During Treatment

SABR treatment requires one week for planning and one week for delivery of the 1 or 3 fractionation schemes. Thus, CT simulation and treatment planning will take place any time before the radiation. SABR will be performed after 1st cycle of Nivolumab infusion. Vital Signs, AE Assessment, Medication Review and Laboratory Review may be performed by a Nurse or Physician.

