Target lesions. All measurable lesions up to a maximum of 2 lesions per organ and 5 lesions in total, representative of all involved organs, should be identified as **target lesions** and recorded and measured at baseline. Target lesions should be selected on the basis of their size (lesions with the longest diameter) and their suitability for accurate repeated measurements (either by imaging techniques or clinically). A sum of the longest diameter (LD) (longest for non-nodal lesions, short axis for nodal lesions) for all target lesions will be calculated and reported as the baseline sum LD. The baseline sum LD will be used as reference by which to characterize the objective tumor response.

Note: Lesions receiving SABR will be called "radiated lesion" which should not be confused with "target lesions" defined here for the for the purpose of radiographic measurement. Radiated lesions and target lesions are mutually exclusive lesions. Therefore, radiated lesions will not be used as target lesions for evaluating response. At least 2 non-CNS measurable lesions are required for enrollment.

Non-target lesions. All other lesions (or sites of disease) including any measurable lesions over and above the 6 target lesions should be identified as **non-target lesions** and should also be recorded at baseline. Measurements of these lesions are not required, but the presence or absence of each should be noted throughout follow-up.

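### The lesions to be irradiated, and so excluded from the target set, may be chosen after nivolumab has started, and no rule locks the target list or scores a patient whose baseline target lesion is later irradiated

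*Combined protocol and SAP*

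**What the plan says.** **How targets are defined.** Section 4.1 states that target "lesions will be selected from non-treated lesions". Section 6.1.2 has them "recorded and measured at baseline" and makes irradiated and target lesions mutually exclusive. Sections 2.1 and 2.4.1 repeat the exclusion for the primary endpoint, RECIST response.

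**How SABR sites are chosen.** Section 4.1.1: "Treating physician will have further discretion in selecting the number and location of sites to treat if multiple sites of disease are present". It prefers the largest feasible sites, symptomatic sites, and sites with a palliative or preventative indication. A site is one "identified by CT scan, or PET/CT, within 4 weeks prior to initiation of SABR". At least one site must be left untreated for response measurement, and it may be irradiated once the patient has progressive disease.

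**When this happens.** Section 2.0: "SABR will be administered to 1-6 sites of metastatic disease one week after the first dose of" nivolumab. Section 4.1: "SABR will be administered to 1-6 sites of metastatic disease on the 2 weeks after the second dose of Nivolumab". Section 4.3 places SABR after the second and before the fourth dose. Section 5.2 places it after the first cycle and adds that "CT simulation and treatment planning will take place any time before the radiation".

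**Scans.** The baseline CT may be up to 6 weeks before registration (5.1.13). The time and events table (5.4) shows only CT simulation before radiation, and the next diagnostic CT at the follow-up visit every 8 to 12 weeks.

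**The concern.** Choosing a lesion for SABR also decides that it does not count in the target sum. If that choice is open after nivolumab has begun, the set of lesions behind the primary endpoint can depend on what happened on treatment. Bad faith is not needed. A lesion that enlarges or becomes symptomatic on nivolumab is a more natural candidate for SABR under the protocol's own preferences, and taking it out of the sum leaves lesions that are on average doing better. The direction is towards a higher RR.

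The trial has one arm, the investigator assesses the tumors (5.3), and the result is compared with a fixed historical rate of 25%. No control group shares the bias. With 19 patients, one or two reclassified patients can decide the test.

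**Working it through.** **1. Reproduce the design.** Section 11.2 gives p0 = 0.25, p1 = 0.50, n = 19, exact binomial test, two-sided 0.2 (taken as 0.1 per tail), 80% power. The tail is P(X ≥ r | n, p) = Σ C(n,k) p^k (1−p)^(n−k), for k from r to n.

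- At n = 19, the smallest r with upper tail at or below 0.1 is r = 8.
- P(X ≥ 8 | 19, 0.25) = 0.0775 (7.7%).
- P(X ≥ 8 | 19, 0.50) = 0.820.
- n = 17 and n = 18 give power 0.686 and 0.760, so 19 is the smallest size from 17 to 21 that reaches 80%. The stated N reproduces.

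**2. Can the site scan fall after dose 1?** Take dose 1 as week 0. The scan window runs from 4 weeks before SABR to SABR. The only dosing interval given is every 3 weeks (1.4.2); 2 and 4 weeks are assumptions, because dosing otherwise follows institutional guidelines.

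| SABR timing | Interval | SABR week | Scan window (weeks) |
|---|---|---|---|
| 2.0: 1 week after dose 1 | any | 1 | −3 to 1 |
| 4.1: 2 weeks after dose 2 | 2 weeks | 2 + 2 = 4 | 0 to 4 |
| 4.1 | 3 weeks | 3 + 2 = 5 | 1 to 5 |
| 4.1 | 4 weeks | 4 + 2 = 6 | 2 to 6 |
| 4.3: after dose 2, before dose 4 | 3 weeks | 3 to 9 | opens between −1 and 5 |

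Section 5.2 gives no week but is also after nivolumab starts. A scan after dose 1 is permitted under every version. Under 4.1 with 3- or 4-week dosing, no pre-dose scan fits the window. Under 2.0 a pre-dose scan can fit, but only if taken within 3 weeks before dose 1, whereas the baseline CT may be up to 6 weeks before registration.

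**3. Does baseline recording close the route?** Section 6.1.2 fixes when targets are recorded. Section 4.1 draws them from lesions that are not treated, and that set is final only when the SABR sites are. If a recorded target is later irradiated, the exclusivity rule in 6.1.2 removes it. No section says whether the baseline sum is then recalculated or how the patient is scored. The reserved-site rule in 4.1.1 keeps one site, so a sole target lesion is protected until progression. Where there are other targets, they are not.

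**4. What a shift would do (illustration).**

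- Worst case: every null trial with exactly 7 responders gains one reclassified patient. The false-positive rate becomes P(X ≥ 7 | 19, 0.25) = 0.0775 + P(X = 7) = 0.0775 + 0.0974 = 0.175.
- If selection raises the null RR (assumed values), P(X ≥ 8 | 19, p) is:

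| Null RR | P(8 or more of 19) |
|---|---|
| 25% (design) | 0.077 |
| 27.5% | 0.123 |
| 30% | 0.182 |
| 35% | 0.334 |
| 40% | 0.512 |

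**The case against.** The strongest reply is that the allocation is already a baseline decision. Section 6.1.2 identifies and measures targets at baseline, and their sum is the reference. Section 3.1 requires both measurable disease at a non-irradiated site and eligibility for SABR to 1 to 6 sites, so the split must be considered before registration. The 4-week phrase sits in the definition of a site and does not order a restaging scan. Planning may take place before nivolumab. The preference for large or symptomatic sites also narrows the discretion.

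Much of this stands as a limit on the point. A reader might infer three stronger things that the documents do not support:

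- **That the physician chooses with early response in view.** No diagnostic CT is scheduled between baseline and the first follow-up at 8 to 12 weeks, and under the Section 2.0 timing a pre-dose scan can be used. On-treatment information is permitted, not shown to be routine.
- **That growing lesions escape response assessment altogether.** They leave the target sum. New lesions and unequivocal progression of non-target lesions still count as progression (6.1.4.2). Whether an irradiated lesion counts as non-target is not stated.
- **That any exclusion of a bulky lesion is outcome-dependent.** The size preference would send many of the largest lesions to SABR from the start, which is legitimate. The exposure is the later switch of a listed target.

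The reply does not supply a lock, a requirement to name SABR lesions before dose 1, or a scoring rule for a switch.

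**Conclusion.** The point holds as a gap in the definition of the primary endpoint. The text permits a baseline target lesion to be reassigned to SABR after nivolumab has started, at the treating physician's discretion, and does not say how to score that patient. The bias, if any, is most plausibly upward.

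Its size is unknown. The documents give no frequency of switching and do not show that selection will follow growth. The 17.5% figure is the extreme case in which every trial with 7 responders gains one patient, and 18.2% rests on an assumed null RR of 30%. Neither estimates this trial's error rate; they show only how little movement a 19-patient test can absorb. The change is a cheap improvement, and the sample size calculation is unaffected.

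**What to change.** **Sections 4.1 and 6.1.2.** Require the lesions planned for SABR and the target lesions to be entered in the CRF from the baseline scan before the first nivolumab dose. Keep that target list for the primary RR. Record any later change with its date and reason. Because 6.1.2 now bars irradiated lesions from use as targets, add a sentence saying that the listed set governs the primary analysis, and state whether irradiated lesions are followed as non-target lesions.

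**Section 11.3.** For patients whose listed target lesion was irradiated, report the RR with two sensitivity analyses:

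1. Count them as non-responders.
2. Drop the lesion from both the baseline and the follow-up sums.

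Both are needed because a listed lesion kept in the sum may shrink from direct radiation. Scoring such patients only on assessments before SABR should not be the primary rule. Scheduled response imaging begins at 8 to 12 weeks, so most would have no such assessment, and 6.1.1 requires two re-evaluations for evaluability.

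**SABR timing.** Sections 2.0, 4.1, 4.3 and 5.2 disagree and must be reconciled. No view is taken here on which is right.

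**Cost.** One CRF page per patient and possibly a slightly lower RR in the non-responder sensitivity analysis. Treatment choice is not restricted, and N stays at 19 (21 with the dropout allowance).

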4.1.2 Planning Constraints and Concerns

The tolerance dose of SABR to the gastrointestinal tract is not established, and patients with metastatic disease involving the esophagus, stomach, intestines, or mesenteric lymph nodes will be eligible only if no other sites of lesions are present that can be safely targeted, and the treating radiation oncologist feels that a sufficiently conservative dose constraints to these organs can be met. Patients with renal or adrenal metastases are potentially eligible if normal tissue constraints are otherwise met.

It is well established that for palliative effect for a painful bone metastasis, a single dose of 8 Gy is usually as effective as 30 Gy [95]. However, in this protocol the goal is not just to relieve pain within an osseous metastasis but also to dramatically debulk the tumor present and induce an immune response, and the higher dose is more likely to accomplish this goal given a higher biological potency [96]. Long term survival after bone metastasectomy has been reported [97]. Irradiation of non-spinal skeletal sites does not generally require specialized techniques of treatment. Metastases in major lower extremity weight-bearing bones should undergo surgical stabilization if there is plain film evidence of cortical erosion.

4.1.3 SABR Treatment Technique

4.1.3.1 Simulation, beam arrangements, tumor prescription dose

Treatment to skeletal lesions and paraspinal lesions may be accomplished with any 3D conformal radiotherapy or intensity-modulated radiotherapy (IMRT) technique suitable for this application with performance specifications adequate to provide proper tumor dose distribution and normal tissue sparing.

At the time of simulation for patients who will receive SABR to the lung and/or liver, the movement of the dome of the diaphragm (superior portion of the liver) is to be observed under fluoroscopy or other acceptable means to estimate respiratory movement during treatment if no

breathing control device is used. Patients will be assessed for suitability for tolerance of a respiratory control device using a breath-hold technique, respiratory gating, or abdominal compression to limit diaphragmatic excursion during respiration. Patients with severe lung disease and patients who cannot tolerate diaphragmatic or breathing control devices for other reasons will be treated without them. A larger margin to account for breathing related intra-fractional organ movement is required.

With the patient is immobilized in a vacuum-type or equivalent body mold, a planning CT scan with 2-5 mm slices is performed. Intravenous contrast is recommended for lesions near mediastinal structures and lesions within the liver. The form of respiratory control to be used during treatment should also be used during the simulation. Oral GI contrast to highlight the stomach and duodenum is recommended for patients with medial liver lesions or lesions of the caudate lobe.

The planning target volume (PTV) is constructed to account for the positional uncertainty of the GTV during treatment. The PTV for each contoured GTV should be at least 5mm larger than the GTV in the axial plane and 1.0 cm larger than the GTV in the cranio-caudal plane. Larger margins may be used in cases where greater motion of the hemi-diaphragm is observed in simulation despite standard maneuvers to diminish motion. For lung SABR the same principles apply; the entire lung volumes are contoured, as are each individual GTV within the lung.

The prescription dose for each lesion is listed in the table in section 4.1.1, prescribed to the periphery of the PTV. There is no restriction on the dose “hotspot” except that it must be located within the PTV. A Linear Accelerator with effective photon energies of ≥ 6 MV is required. The use of a multi-leaf collimator (MLC) or custom blocks are acceptable. A stereotactic relocalization system that relies upon stereoscopic radiographs, implanted fiducials, or near real-time CT based verification will be used. The PTV may be treated with any combination of coplanar or non-coplanar three-dimensional conformal fields, shaped to deliver the specified dose while restricting the dose to the normal tissues. Field arrangements will be determined by the planning system to produce the optimal conformal plan in accordance with volume definitions.

4.1.3.2 Normal Tissue Dose Constraints

In accordance with prior Phase I studies [98], certain normal tissue dose constraints must be respected. The possibility that SABR-induced fibrosis might cause occlusion of large central airways, thus impeding ventilation distal to the occlusion has been well considered [99]. An adjustment to the fractionation scheme may be made if, in the opinion of the treating radiation oncologist, the following conditions apply: (1) the location of a lung lesion is close enough to a large proximal bronchial airway such that occlusion might occur, and (2) compromised ventilation to the segment(s) of lung potentially affected would cause clinically significant adverse consequences. In such a case, the treating radiation oncologist should discuss any proposed dose modifications with the PI to decide whether a regimen of similar biological potency can be safely given.

The same special condition applies in the setting of a patient whose primary disease has been irradiated previously and is present as a site of disease. Since re-irradiation toxicity is a concern, these patients will be considered by the PI on a case-by-case basis and SABR to a site previously irradiated with conventional fractionation within two years is not recommended. Re-irradiation to a site that has received previous SABR is not allowed. Deviations from the intended dose regimen will be documented, with calculations of the BED of the applied regimen included in the patient’s research chart along with documentation of the discussions pertaining to the idiosyncrasies of the case.

The following table lists the specific organ and dose fractionation constraints on normal tissues.

For One Fraction:

Serial Tissue	Volume	Volume Max (Gy)	Max Point Dose	Endpoint (\geq Grade 3)
---------------	--------	-----------------	----------------	----------------------------

			(Gy)**	
Optic Pathway	<0.2 cc	8 Gy	10 Gy	neuritis
Cochlea			9 Gy	hearing loss
Brainstem (not medulla)	<0.5 cc	10 Gy	15 Gy	cranial neuropathy
Spinal Cord and medulla	<0.35 cc <1.2 cc	10 Gy 8 Gy	14 Gy	myelitis
Spinal Cord Subvolume (5-6 mm above and below level treated per Ryu)	<10% of subvolume	10 Gy	14 Gy	myelitis
Cauda Equina	<5 cc	14 Gy	16 Gy	neuritis
Sacral Plexus	<5 cc	14.4 Gy	16 Gy	neuropathy
Esophagus*	<5 cc	11.9 Gy	15.4 Gy	stenosis/fistula
Brachial Plexus	<3 cc	13.6 Gy	16.4 Gy	neuropathy
Heart/Pericardium	<15 cc	16 Gy	22 Gy	pericarditis
Great vessels	<10 cc	31 Gy	37 Gy	aneurysm
Trachea and Large Bronchus*	<4 cc	17.4 Gy	20.2 Gy	stenosis/fistula
Bronchus- smaller airways	<0.5 cc	12.4 Gy	13.3 Gy	stenosis with atelectasis
Rib	<5 cc	28 Gy	33 Gy	Pain or fracture
Skin	<10 cc	25.5 Gy	27.5 Gy	ulceration
Stomach	<5 cc	17.4 Gy	22 Gy	ulceration/fistula
Bile duct			30 Gy	stenosis
Duodenum*	<5 cc <10 cc	11.2 Gy 9 Gy	17 Gy	ulceration
Jejunum/Ileum*	<30 cc	12.5 Gy	22 Gy	enteritis/obstruction
Colon*	<20 cc	18 Gy	29.2 Gy	colitis/fistula
Rectum*	<3.5 cc <20 cc	39 Gy 22 Gy	44.2 Gy	proctitis/fistula
Ureter			35 Gy	stenosis
Bladder wall	<15 cc	12 Gy	25 Gy	cystitis/fistula
Penile bulb	<3 cc	16 Gy		impotence
Femoral Heads	<10 cc	15 Gy		necrosis
Renal hilum/vascular trunk	15 cc	14 Gy		malignant hypertension
Parallel Tissue	Critical Volume (cc)	Critical Volume Dose Max (Gy)		Endpoint (≥Grade 3)
Lung (Right & Left)	1500 cc	7 Gy		Basic Lung Function
Lung (Right & Left)	1000 cc	7.6 Gy	V-8Gy <37%	Pneumonitis
Liver	700 cc	11 Gy		Basic Liver Function
Renal cortex (Right & Left)	200 cc	9.5 Gy		Basic renal function

For Three Fractions:

Serial Tissue	Volume	Volume Max (Gy)	Max Point Dose (Gy)**	Endpoint (≥Grade 3)
Optic Pathway	<0.2 cc	15.3 Gy	17.4 Gy	neuritis
Cochlea			14.4 Gy	hearing loss
Brainstem (not medulla)	<0.5 cc	15.9 Gy	23.1 Gy	cranial neuropathy
Spinal Cord and medulla	<0.35 cc <1.2 cc	15.9 Gy 13 Gy	22.5 Gy	myelitis
Spinal Cord Subvolume (5-6 mm above and below level)	<10% of subvolume	18 Gy	22.5 Gy	myelitis

treated per Ryu)				
Cauda Equina	<5 cc	21.9 Gy	25.5 Gy	neuritis
Sacral Plexus	<5 cc	22.5 Gy	24 Gy	neuropathy
Esophagus*	<5 cc	17.7 Gy	25.2 Gy	stenosis/fistula
Brachial Plexus	<3 cc	22 Gy	26 Gy	neuropathy
Heart/Pericardium	<15 cc	24 Gy	30 Gy	pericarditis
Great vessels	<10 cc	39 Gy	45 Gy	aneurysm
Trachea and Large Bronchus*	<5 cc	25.8 Gy	30 Gy	stenosis/fistula
Bronchus- smaller airways	<0.5 cc	18.9 Gy	23.1 Gy	stenosis with atelectasis
Rib	<5 cc	40 Gy	50 Gy	Pain or fracture
Skin	<10 cc	31 Gy	33 Gy	ulceration
Stomach	<5 cc	22.5 Gy	30 Gy	ulceration/fistula
Bile duct			36 Gy	stenosis
Duodenum*	<5 cc <10 cc	15.6 Gy 12.9 Gy	22.2 Gy	ulceration
Jejunum/Ileum*	<30 cc	17.4 Gy	27 Gy	enteritis/obstruction
Colon*	<20 cc	24 Gy	34.5 Gy	colitis/fistula
Rectum*	<3.5 cc <20 cc	45 Gy 27.5 Gy	49.5 Gy	proctitis/fistula
Ureter			40 Gy	stenosis
Bladder wall	<15 cc	17 Gy	33 Gy	cystitis/fistula
Penile bulb	<3 cc	25 Gy		impotence
Femoral Heads	<10 cc	24 Gy		necrosis
Renal hilum/vascular trunk	15 cc	19.5 Gy		malignant hypertension
Parallel Tissue	Critical Volume (cc)	Critical Volume Dose Max (Gy)		Endpoint (≥Grade 3)
Lung (Right & Left)	1500 cc	10.5 Gy		Basic Lung Function
Lung (Right & Left)	1000 cc	11.4 Gy	V-11Gy<37%	Pneumonitis
Liver	700 cc	17.1 Gy		Basic Liver Function
Renal cortex (Right & Left)	200 cc	15 Gy		Basic renal function

*Avoid circumferential irradiation.

** "point" defined as 0.035cc or less

Exceeding these dose tolerances by more than 2.5% constitutes a minor protocol violation.

Exceeding these dose tolerances by more than 5% constitutes a major protocol violation.

